4.2.1.4 Sensitivity Analyses

Several sensitivity analyses may be performed to assess the robustness of the primary analysis to changes among stratification factors as randomized, analysis population, missing data and definition of the primary endpoint (refer to Table 4.4 and Section 4.1.1).

4.2.1.4.1 Sensitivity Analysis to Stratification Factors

The assumption of homogeneity of the OR over the actual strata will be tested by the Breslow-Day statistic at a 10% significance level for each pairwise comparison to placebo.

In the event of non-homogeneity of the OR for a particular test, the corresponding treatment OR will be calculated separately with its 95% confidence interval for each stratum. Owing to the limited sample size in each stratum, no p-value will be reported, the main purpose of this assessment being to evaluate the relative magnitude of the treatment difference in each stratum.

In case of a large number of stratification errors, the primary analysis may be repeated as described in Section 4.2.1.3 but using the per randomized stratum i.e. as entered by the sites into the IRT system at the randomization.

4.2.1.4.2 Sensitivity Analyses to Analysis Population

Sensitivity analyses will be performed identically to the primary analysis but using the following populations: MITT12 and PP12.

4.2.1.4.3 Sensitivity Analyses to Missing Data

The primary analysis may be replicated using the ITT population:

- with missing data being imputed with:
 - LOCF (see Section 4.1.1.3),
 - MI (see Section 4.1.1.4)
 - Tipping point analysis (see Section 4.1.1.5)
- on complete cases (see Section 4.1.1.1)
(refer to Table 4.4 for further details about the pre-planned analyses).

In addition, the extent of missing IGA data will be summarized by visit and treatment group.

Figures of individual raw IGA as well as mean raw IGA may be provided for the subgroups of complete cases and cases with missing IGA assessment at Week 12, by treatment group and over time up to Week 12.

4.2.1.4.4 Sensitivity Analysis to Endpoint Definition

To assess the robustness of inferences to the definition of the primary endpoint, the same analysis as in Section 4.2.1.3 will be repeated by considering a different definition for an IGA responder: “complete IGA response” where a complete IGA response is defined as an IGA score of 0 and with an IGA reduction from baseline of 3 points or more.

4.2.2 Secondary Analyses

All subjects in the ITT population will be included in the secondary efficacy analyses.

The main estimands of the secondary objectives of longer-term efficacy after Week 12:

- for the binary endpoint IGA (and the key secondary endpoints PASI 75 / PASI 90 / PASI 100) is the difference in response proportions between treatment conditions at:
 - Week 24,
 - Week 36,
 - Week 48
- for the continuous endpoint PASI score (and the other secondary endpoint percentage of total BSA affected by plaque-type psoriasis) is the difference in means between treatment conditions in the change from baseline to:
 - Week 24,
 - Week 36,
 - Week 48

in the ITT population regardless of whether or not escalating to the M1095 120 mg from Week 12 or having dose held at Week 24 had occurred.

In the next subsections, the analysis of the secondary variables will be handled according to the type of variables: binary for proportions, categorical for shift from baseline, or continuous for change from baseline and/or percent change variables.

4.2.2.2 Descriptive and Inferential Analyses

4.2.2.2.1 Binary and Categorical Variables

The proportions of the binary variables will be summarized by treatment group at each visit up to Week 52. Pairwise comparisons vs. placebo and pairwise comparisons across M1095 treatment arms will be made at each visit up to Week 12 and at Weeks 24, 36 and 48 using the CMH test of 2-by-2 tables stratified by actual prior use of biologics (yes/no) and body weight stratum (≤ 90 kg, > 90 kg) in the same way as for the primary analysis (please refer to Section 4.2.1.3). No formal statistical testing will be performed between M1095 treatment arms and Secukinumab as the Secukinumab arm is for reference only. However, Secukinumab will be compared to placebo using the same methodology. In case of a large number of stratification errors, the key secondary analyses might be repeated as described in Section 4.2.1.3 but using the per randomized stratum as entered into the IRT system by the sites.

The assumption of homogeneity of association between treatment and the binary variables in the different actual strata will be tested at Weeks 12, 24, 36 and 48 for all pairwise comparisons M1095 vs. placebo at 10% significance level using the Breslow-Day test as explained in Section 4.2.1.4.

For the categorical analyses, the proportion and number of subjects in each IGA category at a given visit from baseline will be presented by treatment group and over time at each visit up to Week 12 for the induction period, from Week 12 to Week 24 for the maintenance/escalation period and from Week 24 to Week 48 for the response assessment/dose hold period.

Bar plots and line plots of the responder rates with 95% CI will be provided by treatment group and over time up to Week 48 overall.

The binary secondary efficacy variables will be listed by treatment group and over time.

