#### Secondary analyses:

Secondary efficacy and QoL endpoints will be compared between treatments at each visit up to Week 48 using the CMH test for binary endpoints and an Analysis of Covariance (ANCOVA) model for changes from baseline.

Safety data will be summarized in the Safety Analysis Set by treatment and over time, for each treatment period separately and overall.

Exploratory analyses:

Exploratory analyses of efficacy will be made for (i) all subjects who were dose-escalated at Week 12, and (ii) all subjects who had active treatment withheld following an IGA score of 0 at Week 24.

Subgroup analyses:

Subgroup analyses of key efficacy and safety data will be performed as appropriate by geographical region, prior biological use, weight category, gender and geriatric status.

Interim analyses:

[figure not shown]
An independent Data Monitoring Committee (DMC) will be established to perform and review interim analyses during the study. The DMC will be operational prior to enrolment of the first subject into the study. The composition and operation of the DMC will be described in a DMC charter. The charter will also detail how the communication between the DMC and the sponsor will be firewalled to preserve the blinding and integrity of the study.

The DMC will closely monitor the safety and tolerability data throughout the trial. No formal analysis of efficacy is planned during the double-blind, placebo-controlled 12-week induction phase.

An unblinded interim analysis of 12-week data will occur at the completion of the Week 12 period, while the study is still ongoing. These data will be shared with firewalled individuals who are not directly involved in the conduct of the study.

A second interim analysis will occur at the completion of the Week 24 period. All investigators and subjects will remain blinded to treatment assignments until the last subject completes the study and the final database lock occurs. Once the second interim database lock has occurred after Week 24, the sponsor study team will be unblinded.

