##### 9.4.1 Efficacy Analyses

Endpoint	Statistical Analysis Methods
Primary	
The primary endpoint is achievement of an IGA score of 0 or 1 at Week 12. Response rates of IGA score of 0 or 1 at Week 12 will be used to compare the treatment arms. The response rate of IGA score of 0 or 1 at Week 12 is defined as the proportion of subjects at Week 12 with an IGA score of 0 or 1 and with an IGA reduction from baseline of 2 points or more. Baseline IGA score is the last score prior to the first dose of study medication. Any missing IGA score of 0 or 1 response will be imputed as a non-response.
 
The primary analysis will be based on the ITT Analysis Set. The primary treatment comparisons will be made using the two-sided Cochran-Mantel-Haenszel (CMH) test stratified by prior biologic use and body weight stratum.

Secondary	
The key secondary endpoints are the PASI 75, PASI 90 and PASI 100 at Week 12. Secondary efficacy and QoL endpoints will be compared between randomized treatments in the ITT Analysis Set at each visit up to Week 12 and at Weeks 24, 36 and 48 using the CMH test for binary endpoints and for the shift from baseline in IGA and an Analysis of Covariance (ANCOVA) model

	
for changes from baseline. The ANCOVA model will include treatment, prior biologic use and weight stratum as factors and the baseline value as a covariate.
 
Descriptive summaries will be provided in tabular and graphical formats by treatment and over time.
 
Analysis of the primary and key secondary endpoints will also be performed using the MITT and the PP populations. The impact of missing data on efficacy results will be assessed using multiple imputation, last-observation carried forward and worst-case imputation methods.

Exploratory	Exploratory analyses of efficacy will be made for subjects who (i) were dose-escalated at Week 12, and (ii) who stopped treatment following IGA score of 0 at Week 24.

For the primary and secondary endpoints, comparisons will be made to placebo (all arms), and between the M1095 treatment arms. Dose response and dosing frequency response trend testing will be performed involving selected M1095 arms and placebo. No formal statistical testing will be done between M1095 treatment arms and secukinumab as the secukinumab arm is for reference only. Secukinumab will be compared to placebo using the same methods as the primary analysis.

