			
Section 4.2.1.4.3 Sensitivity Analyses to Missing Data: Clarification of how the extent of missing IGA data will be summarized.
 
Section 4.2.2.2.1 Binary and Categorical Variables:
 
 • Addition of a sensitivity analysis of the key secondary endpoints in case of a large number of stratification errors. • Removal of the assessment of the homogeneity assumption because this assessment is covered by the subgroup analyses. • Removal of the pairwise comparisons for the shift analyses to keep all possible shift categories. 
Section 4.2.3.1.1 Variables and Section 4.2.3.2.1 Variables: Clarification of the IGA categories for the shift analysis.
 
Section 4.3 Quality of Life: Use of the actual stratification factors for all analyses using an ANCOVA.
 
Section 4.9.2.1 Vital Signs: Clarifications of the way to identify vital signs abnormalities.
 
Section 4.12 Subgroup Analyses: Clarification of the subgroup analyses that can be used for sensitivity analyses due to the change of efficacy analyses.
 
Editorial and administrative changes have been made throughout the document.

24-SEP-19	Prior to unblinding of study statistician, programmers and designated sponsor team members at Week 24 (second Interim Analysis)	The SAP was amended to clarify some points.	
Section 2 Interim Analyses:
 
 • Clarification of tasks to be performed for each designated role (study statistician, statistical programmers and designated sponsor team members). • Table 2.1: Clarification that shift analysis from baseline in IGA (secondary endpoint) as well as PK and immunogenicity analyses (exploratory endpoint) will not be reported after Week 24 for Interim Analysis 2. 
Section 4.1.1 Imputation Methods for Missing Data (Table 4.4):
 
 • Correction of the imputation method of the secondary analysis of PASI responses and IGA score of 0 or 1 from Week 24 in the MITT48

Date	Time point	Reason for update	Section title impacted (Current number): Outline of change

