1.3.2 Secondary Objectives

Type of Objective	Study Objective
Key Secondary Objectives	
 To evaluate the efficacy of four dose regimens of M1095 compared to placebo during a 12-week treatment period on secondary endpoints: Psoriasis Area and Severity Index (PASI) 75, PASI 90, PASI 100, change in PASI and shift in IGA.
Secondary Objectives	
 To assess the dose-regimen efficacy relationship for M1095 after 12, 24, 36 and 48 weeks of treatment. To evaluate the longer-term efficacy of M1095 at Week 24 and at Weeks 36 and 48. To assess the safety and tolerability of M1095.

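### The protocol specifies a CMH test for the shift from baseline in IGA; the SAP only describes the shift, so IGA 0/1 response is the only IGA endpoint tested between M1095 doses

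*SAP*

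**What the plan says.** **Protocol.** Section 9.4.1 analyses the secondary endpoints in the ITT set, at every visit to Week 12 and then at Weeks 24, 36 and 48. The method is given as "using the CMH test for binary endpoints and for the shift from baseline in IGA". For primary and secondary endpoints, "comparisons will be made to placebo (all arms), and between the M1095 treatment arms". The synopsis is less specific. It has the tests made "using the CMH test for binary endpoints and an Analysis of Covariance (ANCOVA) model for changes from baseline" and does not name the shift.

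**SAP.** Section 1.3.2 sets a key secondary objective of efficacy against placebo on endpoints that end with "PASI 90, PASI 100, change in PASI and shift in IGA". Table 4.5 keeps the shift as a secondary categorical variable. In Section 4.2.2.2.1 the inferential text covers binary variables in 2-by-2 tables: "Pairwise comparisons vs. placebo and pairwise comparisons across M1095 treatment arms will be made at each visit up to Week 12", and again at Weeks 24, 36 and 48. For the shift the method is: "For the categorical analyses, the proportion and number of subjects in each IGA category at a given visit from baseline will be presented". No test follows.

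The SAP revision history (17 July 2019) gives the reason: "Removal of the pairwise comparisons for the shift analyses to keep all possible shift categories". I cite it only for the reason. The mismatch is between the current protocol and the current SAP text.

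**The concern.** Two things are at stake.

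First, consistency. An objective to evaluate efficacy against placebo on the IGA shift has no comparison behind it, although the protocol names the method. The logged reason does not require this. A CMH row-mean-scores statistic uses every IGA level, so keeping all categories and testing them are compatible.

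Second, dose information on the primary scale. The dose-regimen relationship is a stated secondary objective. The sample-size section assumes IGA 0/1 rates above 88% on drug. If that holds, most of the difference between doses lies between IGA 0 and IGA 1, and the 0/1 response ignores that split.

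**Working it through.** **Step 1. Which IGA variables does the SAP test, and against what?**

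| IGA variable | SAP section | Against placebo | Between M1095 arms |
|---|---|---|---|
| IGA 0/1 response | 4.2.1.3, 4.2.2.2.1 | CMH | CMH |
| Complete response (IGA 0), Week 12 | 4.2.1.4.4 | CMH | none |
| Time to first response or first complete response | 4.2.2.2.2 | Kaplan-Meier description | none |
| Shift from baseline | 4.2.2.2.1 | counts and proportions | counts and proportions |

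Section 4.2.1.4.4 says that "a complete IGA response is defined as an IGA score of 0 and with an IGA reduction from baseline of 3 points or more". It repeats the analysis of 4.2.1.3, where all four comparisons are with placebo. Entry requires IGA of 3 or 4, so for eligible subjects complete response is simply IGA 0, and response is simply IGA 0 or 1.

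**Step 2. Reproduce the plan's own power.** Inputs from Protocol 9.2 and SAP Section 5: n = 50 per arm, two-sided 0.05, two-group chi-square.

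Power = Φ{ [ |p1 − p2|·√n − 1.96·√(2p̄(1 − p̄)) ] / √(p1(1 − p1) + p2(1 − p2)) }

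- PASI 100, 45% against 72%: p̄ = 0.585; (0.27 × 7.071 − 1.96 × 0.697) / 0.670 = 0.811; Φ = 0.791. The plan states about 79%.
- IGA 0/1, 88% against 7%: above 0.999. The plan states above 99%.

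**Step 3. Same formula for IGA 0/1 between doses, lower arm at 88%.**

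- Against 90%: (0.02 × 7.071 − 1.96 × 0.442) / 0.442 = −1.64; power 0.05.
- Against 92%: power 0.10.
- Against 95%: (0.07 × 7.071 − 1.96 × 0.394) / 0.391 = −0.71; power 0.24.
- Against 88% there is no difference to find. The simulated stratified CMH rejects in 0.05 of trials, which is the false-positive rate.

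If the lower dose misses the planning rate, power rises: 0.29 for 80% against 90%, and 0.71 for 70% against 90%.

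**Step 4. What an ordinal test would give.** The documents contain no IGA category distribution, so the ones below are assumptions. They let IGA 0 follow the PASI 100 planning rates. Simulation: 20,000 trials per scenario, 50 per arm, one stratum, CMH = (N − 1)r². The modified ridit score for a category is (number in lower categories + (number in category + 1)/2)/(N + 1).

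| IGA 0/1/2/3/4, lower vs higher dose (%) | IGA 0/1 | Ordinal, ridit | Ordinal, integer | IGA 0 alone |
|---|---|---|---|---|
| 45/43/8/3/1 vs 72/20/5/2/1 | 0.10 | 0.73 | 0.53 | 0.80 |
| 45/43/8/3/1 vs 72/23/3/1.5/0.5 | 0.23 | 0.79 | 0.68 | 0.80 |
| 60/28/8/3/1 vs 72/20/5/2/1 | 0.10 | 0.24 | 0.19 | 0.24 |

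The third row matters because Protocol 4.3 simulates PASI 100 at 30 mg between 45% and 60%.

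**Step 5. Spread.** A separate simulation used four strata, integer scores and six assumed pairs of distributions. Ordinal power ran from 0.32 to 0.95. The gain over IGA 0/1 ran from 0.06 (45% vs 72% clear, 88% vs 100% IGA 0/1) to 0.71 (45% vs 85% clear, 88% vs 95% IGA 0/1).

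**The case against.** The strongest reply is that this is a recorded, reasoned choice about an endpoint the trial does not lean on.

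- The removal is logged before the first unblinding. Protocol 9.0 requires an amendment only for a principal feature; other changes are justified in the study report. This stands, and nothing suggests the change was driven by results. It governs how a change is reported, though, and does not supply an analysis for an objective the SAP still lists.
- Protocol 9.4.1 names PASI 75, 90 and 100 at Week 12 as its key secondary endpoints, and Table 4.5 gives that label only to the PASI responses. This stands and limits the severity.
- Against placebo the planned power on IGA 0/1 exceeds 99%, and IGA 0 is tested as well. This stands: restoring the shift test there is mainly fidelity to the protocol.
- Dose discrimination is covered elsewhere. The plan calls PASI 100 more discriminating. PASI 75, 90 and 100 and percent change in PASI are all compared between M1095 arms. This stands. A reader might infer that the trial cannot separate doses; the documents do not support that.
- A reader might also infer that IGA 0/1 will sit at its ceiling in every M1095 arm. The documents do not show that. The rate above 88% is a planning assumption. The 88-100% range in Protocol 2.3 is an sPGA result from a three-dose phase 1 regimen. The Week 12 escalation rule itself provides for non-responders at 30 and 60 mg.
- IGA 0 alone does about as well as the ordinal test, or better, in all three scenarios of the first table. This stands and belongs in the remedy. It would not by itself restore the shift analysis.

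**Conclusion.** The point holds, at modest size. The protocol's CMH test for the IGA shift is absent from the SAP, the SAP still lists the shift as a key secondary objective, and IGA 0/1 is the only IGA endpoint tested between M1095 doses. Near the planning rates that endpoint separates doses weakly: about 5% to 24% power for 88% against 88-95%, the low end being no more than the false-positive rate.

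Restoring an ordinal test would raise between-dose power on the IGA scale to about 73-79% with ridits, or 53-68% with integer scores, at 45% against 72% clear. At 60% against 72% it would reach only about 25%. These gains rest on assumed category distributions and on IGA 0 following PASI 100. The primary analysis is unaffected, and PASI 100 keeps about 79% planned power between the highest and lowest doses.

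**What to change.** 1. In SAP 4.2.2.2.1, compare post-baseline IGA (0 to 4) with the CMH row-mean-scores test, against placebo and between M1095 arms, at the visits in Protocol 9.4.1: each visit to Week 12 and Weeks 24, 36 and 48. Fix the scores in advance, for example modified ridits, because the result depends on them.
2. Stratify by prior biologic use and weight category, and by baseline IGA (3 or 4) where stratum sizes allow, so that it remains a shift analysis. That makes 2 × 2 × 2 = 8 strata for about 100 subjects per pairwise comparison, 12.5 on average, so state in advance when baseline IGA is dropped.
3. Use the LOCF rule that Table 4.4 already gives for the shift, and keep the shift tables as display.
4. Extend the Week 12 complete IGA response analysis in 4.2.1.4.4 to the comparisons between M1095 arms.
5. State that comparisons at Week 24 and later are between randomized strategies: 30 and 60 mg non-responders escalate at Week 12 and the placebo arm moves to M1095.

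The cost is a few sentences, a PROC FREQ option and a few more unadjusted p-values, in a plan that already makes its pairwise comparisons without adjustment. Date the change against the unblinding steps. If the test is not restored, state the departure from Protocol 9.4.1 and its reason, and reconcile SAP 1.3.2 with the descriptive method.

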4.2.2.2.2 Time-to-event Variables

Time-to-event variables will be presented by treatment group with tables of Kaplan-Meier (KM) estimates as well as KM curves. For KM curves, the number of subjects that are still at risk (Pocock et al, 2012) will also be displayed under the time axis. In addition, the following descriptive statistics will be presented by treatment group: the number and percentage of IGA response, complete IGA response and censored data at each visit and the median time (or other estimable percentile (say 75%) if median is not estimable) to IGA response or complete IGA response along with its 95% confidence interval.

4.2.2.2.3 Continuous Variables

The raw PASI score, absolute change and percent change from baseline in PASI score will be presented by treatment group and over time for all visits up to Week 52 using summary statistics and listings. Mean of change from baseline in PASI and its associated standard error will be displayed graphically over time by treatment group.

For the percent change in PASI, treatment comparisons vs. placebo and between M1095 treatment groups will be tested at each specified visit up to Week 48. The treatment LSM along with the corresponding SE, 95% CI and the LSM differences along with its SE, 95% CI and p-value will be obtained at each visit separately using an analysis of covariance (ANCOVA) model. The ANCOVA will include the planned treatment group, actual prior biologic and weight stratum as factors and the baseline value as a covariate. The residuals from the ANCOVA model will be examined to check that the assumptions of normality, independence and homoscedasticity hold.

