## 9.2 Sample Size Determination

A sufficient number of subjects will be screened, so that a total of approximately 300 subjects will be randomized (approximately 50 per treatment group.)

With this sample size, the study has >99% power to detect a statistically significant difference between any treatment arm and placebo in the IGA score of 0 or 1 rate at Week 12, with a two-sided, unadjusted type I error of 0.05. These calculations assume IGA score of 0 or 1 rates of >88% for study drug and ≤7% for placebo. As this is a phase 2 study, there will be no adjustments for multiplicity.

Exploratory analyses between the different dose levels of M1095 will also be performed. The PASI 100 response rate offers more discriminatory potential for this. Phase 1 data and response simulations give a PASI 100 response rate at Week 12 varying from 45 to 72%. With the sample size of 50 subjects per group, based on these assumed PASI 100 response rates at Week 12, the comparison between the highest and lowest M1095 doses has approximately 79% power.

Power calculations have been performed with SAS v.9.4 Proc Power using the methodology for a two-group chi square test of equal proportions.

Randomization will be stratified by prior biologic use (yes, no) and weight (≤90kg, >90kg).

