(6) - Secukinumab 300 mg at Week 0, 1, 2, 3, 4, 8 (and 12 and Q4W)	Secukinumab
(2) - M1095 30 mg at Week 0, 2, 4, 8 (2a) and Q4W if no escalation at Week 12 (2b) and M1095 120 mg Q4W if escalation at Week 12	30mg (x4), Q4
(3) - M1095 60 mg at Week 0, 2, 4, 8 (3a) and Q4W if no escalation at Week 12 (3b) and M1095 120 mg Q4W if escalation at Week 12	60mg (x4), Q4
(4) - M1095 120 mg at Week 0, 2, 4, 8 (and 12 and Q8W)	120mg (x4), Q8
(5) - M1095 120 mg Q2W at Week 0, 2, 4, 6, 8, 10 (and 12 and Q4W)	120mg (x6), Q4
	Total M1095 ^c

a: Subjects will be assigned to a treatment group based on the actual treatment they received most during the overall period for all treatment groups except for (1), (2b) and (3b). Regarding (2b) and (3b), subjects will be assigned to a treatment group based on the actual treatment they received most during the induction period.

b: Plac/120 mg (x4), Q4 include all subjects who were mostly administered M1095 120 mg from Week 12 to Week 44 having received placebo during the induction period. The data will only be presented from Week 12 onwards for this treatment group.

c: Total M1095 will include all subjects who received M1095 at any time during the study i.e. (1), (2), (3), (4) and (5).

All pairwise treatment comparisons will be two-sided at the 5% level, without adjustment for multiplicity unless otherwise specified.

All primary/secondary efficacy and exploratory QoL endpoints will be presented in tables including visits from Week 0 to Week 52 as follows: 0, **1, 2, 3, 4, 6, 8, 10, 12**, // 14, 16, 20, **24**, // 28, 32, **36**, 40, 44, **48** and 52 (each week number, written in bold, indicates the weeks, at which the pairwise treatment comparisons will be made and // indicates the boundary for the study periods). In regard to interim analyses, only visits up to Week 12 will be included for IA1. IA2 will include data up to Week 24 for all subjects and beyond Week 24 for some subjects depending on the cut-off date (see Section 2). The analyses may be split by period or by combined periods depending on the tables produced for IA1 and IA2.

For all efficacy and quality of life analyses unless specified otherwise, baseline will be defined as the last non-missing assessment prior to the first dose of study medication (planned at Week 0).

For safety analyses, baseline will be defined differently according to the treatment period:

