4.12.2.3 Safety Variables

The number and percentage of subjects with AESI will be summarized by treatment group classed by SOC and PT for each category of the subgroup for the induction and overall period (refer to Section 4.9.2.5).

REDACTED COPY

This document must not be used to support any marketing authorization application or any variation or extension of such application

5 Sample Size Calculation

A sufficient number of subjects will be screened, so that a total of approximately 300 subjects will be randomized (approximately 50 per treatment group).

With this sample size, the study has > 99% power to detect a statistically significant difference between any treatment arm and placebo in the IGA score of 0 or 1 rate at Week 12, with a two-sided, unadjusted type I error of 0.05. These calculations assume IGA score of 0 or 1 rates of > 88% for study drug and \leq 7% for placebo. As this is a phase 2 study, there will be no adjustments for multiplicity.

Exploratory analyses between the different dose levels of M1095 will also be performed. The PASI 100 response rate offers more discriminatory potential for this. Phase 1 data and response simulations give a PASI 100 response rate at Week 12 varying from 45 to 72%. With the sample size of 50 subjects per group, based on these assumed PASI 100 response rates at Week 12, the comparison between the highest and lowest M1095 doses has approximately 79% power.

Power calculations have been performed with SAS v.9.4 Proc Power using the methodology for a two-group chi square test of equal proportions.

Randomization will be stratified by prior biologic use (yes, no) and weight (\leq 90 kg, > 90 kg).

6 Reference List

Abraha, Iosief & Montedori, Alessandro. (2010). Modified intention to treat reporting in randomised controlled trials: Systematic review. *BMJ (Clinical research ed.)*. 340. c2697. 10.1136/bmj.c2697.

Committee for Medicinal Products for Human Use, 2017. Guideline on immunogenicity assessment of therapeutic proteins. London: European Medicines Agency.

Committee for Proprietary Medicinal Products (CPMP), Points to Consider on Adjustment for Baseline Covariates (2003). *Stat Med*, 23(5), pp.701-709.

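### The ANCOVA of percent PASI change pools one residual variance over arms expected to differ in spread by Week 12, and its homoscedasticity check has no stated consequence

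*SAP*

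**What the plan says.** For percent change in PASI, SAP 4.2.2.2.3 states that "treatment comparisons vs. placebo and between M1095 treatment groups will be tested at each specified visit up to Week 48". LS means, differences, SEs, 95% CIs and p-values come from an ANCOVA fitted at each visit separately: "The ANCOVA will include the planned treatment group, actual prior biologic and weight stratum as factors and the baseline value as a covariate". Protocol 9.4.1 gives the same model: "The ANCOVA model will include treatment, prior biologic use and weight stratum as factors and the baseline value as a covariate". Under SAP 4.1, "All pairwise treatment comparisons will be two-sided at the 5% level, without adjustment for multiplicity unless otherwise specified".

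Neither document names arm-specific variances, robust SEs, a transformation or a rank test. The one safeguard is a diagnostic: "The residuals from the ANCOVA model will be examined to check that the assumptions of normality, independence and homoscedasticity hold". It has no criterion and no alternative analysis.

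On expected response, Protocol 9.2 says that phase 1 data and simulations "give a PASI 100 response rate at Week 12 varying from 45 to 72" per cent, and SAP section 5 repeats this. Protocol 4.3 ties the two ends to doses: about 45-60% for 30 mg and 72-85% for 120 mg every two weeks. SAP 4.2.2.1 defines PASI 100 as a score of 0, so each such subject has a percent change of exactly -100. Assumed placebo IGA 0/1 response is at most 7% (Protocol 9.2).

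**The concern.** An ordinary ANCOVA estimates one residual variance from all arms in the model and uses it in every contrast. It is right for a given pair only if that pair's average variance equals the average over all arms.

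Here unequal variance is foreseeable. By Week 12 about half or more of each M1095 arm should sit on one value, the share on that value should rise with dose, and few placebo subjects should be near it. If placebo is the most variable arm, its variance inflates the SE of every M1095-versus-M1095 contrast, while the tighter active arms shrink the SE of contrasts against placebo.

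The stake is calibration at the later visits up to Week 12: intervals that do not cover at 95%, and lost power between doses, where the dose-regimen relationship is a secondary objective. Because the check leads nowhere in the text, any remedy would be chosen after seeing the residuals.

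**Working it through.** **The plan's own figure.** PASI 100 of 45% against 72%, 50 per arm, two-sided 0.05, chi-square test. The mean proportion is 0.585, so z = [0.27√50 − 1.96√(2 × 0.585 × 0.415)] / √(0.45 × 0.55 + 0.72 × 0.28) = (1.909 − 1.366)/0.670 = 0.81, and power is 79%, as stated. That figure is for the responder comparison. The documents give no power or SD for percent PASI change.

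**Inputs from the documents.** Six arms, about 50 each; 45% at -100% for 30 mg and 72% for 120 mg (x6).

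**Assumptions.** Shares at -100%: 55% for 60 mg, 65% for 120 mg (x4), 50% for secukinumab. The remaining subjects exceed -100 by an exponential amount with mean m = 10 to 25 points. Placebo SD s = 20 to 35. All six arms are in the model.

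**Formulas.** An arm with share p at the floor has variance m²(1 − p²). With equal arm sizes the pooled variance is the mean of the six:

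V = [m²(0.7975 + 0.6975 + 0.5775 + 0.4816 + 0.75) + s²]/6 = (3.304m² + s²)/6

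For arms i and j, model SE / true SE = √{V / [(vᵢ + vⱼ)/2]} = r, and coverage of a nominal 95% CI is about 2Φ(1.96r) − 1.

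**Worked corner, m = 10, s = 35.** V = (330.4 + 1225)/6 = 259.2. For 30 mg versus 120 mg (x6): (79.75 + 48.16)/2 = 64.0, r = √(259.2/64.0) = 2.01. For placebo versus 120 mg (x6): (1225 + 48.16)/2 = 636.6, r = 0.64, coverage 79%.

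| m | s | V | r, 30 mg vs 120 mg (x6) | r (coverage), placebo vs 30 mg | r (coverage), placebo vs 120 mg (x6) |
|---|---|---|---|---|---|
| 10 | 20 | 121.7 | 1.38 | 0.71 (84%) | 0.74 (85%) |
| 10 | 35 | 259.2 | 2.01 | 0.63 (78%) | 0.64 (79%) |
| 25 | 20 | 410.8 | 1.01 | 0.96 (94%) | 1.08 (97%) |
| 25 | 35 | 548.3 | 1.17 | 0.80 (88%) | 0.85 (90%) |

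**Where the direction turns.** Let S be the sum of the five active variances and v that of the active arm compared. The placebo contrast is too narrow only if s² > (S − 3v)/2. For 120 mg (x6) with m = 25 this is (2065 − 903)/2 = 581, so s must exceed 24. In the third row s is 20 and the interval is too wide. In that row 30 mg versus 60 mg is slightly too narrow: √(410.8/467.2) = 0.94.

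**Power, 30 mg versus 120 mg (x6).** The true difference is (0.55 − 0.28)m = 0.27m, or 2.7 to 6.75 points. Simulating these settings gave about 2-40% power with the pooled variance and 41-43% with arm-specific variances.

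**A second data model.** A six-arm ANCOVA with strata and baseline was simulated 1,500 times per scenario, with active arms built from PASI 75/90/100 rates (SDs about 20, 17, 15, 12 and 10 for secukinumab, 30 mg, 60 mg, 120 mg (x4) and 120 mg (x6)):

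| Placebo SD | Contrast | Pooled SE | Robust (HC2) SE | Pooled result | Robust result |
|---|---|---|---|---|---|
| 25 | placebo vs 30 mg | 3.44 | 4.27 | 88% coverage | 95% coverage |
| 25 | 30 mg vs 120 mg (x6) | 3.44 | 2.78 | 60% power | 78% power |
| 35 | placebo vs 30 mg | 3.98 | 5.47 | 85% coverage | 95% coverage |
| 35 | 30 mg vs 120 mg (x6) | 3.98 | 2.79 | 42% power | 76% power |

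Robust SEs gave 93-96% coverage for every contrast in every scenario. Every Week 12 test against placebo rejected with either SE. The turning point for placebo versus 120 mg (x6) was a placebo SD of about 21, or about 26 with wider active SDs.

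**After Week 12.** Protocol 6.6.1 moves the placebo arm to M1095 120 mg. Simulated at Week 24, its contrast with 30 mg had pooled and robust SEs of 2.93 and 2.92, and with 120 mg (x6) 2.93 and 2.18, so the pooled interval there is too wide.

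**The case against.** The strongest reply is that every size above rests on SDs the documents do not give. The assumed range includes settings with almost no distortion and one where the direction reverses. This stands: a reader might infer that intervals against placebo are certainly too narrow and those between doses certainly too wide, and the documents do not support that. They support unequal spread, not its amount. The lowest power figures also come from an extreme corner, where the true dose difference is only 2.7 points.

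Second, dose discrimination rests mainly on PASI 100, which Protocol 9.2 calls more discriminating and which SAP 4.2.2.2.1 tests by stratified CMH. This stands too. The percent-change contrasts are secondary, and under the first data model even the repaired ANCOVA reaches only 41-43% power. It would be wrong to say that the plan cannot see dose differences.

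Third, a reader might extend the placebo argument to Weeks 24, 36 and 48, or to the plotted error bars. Neither follows. No arm receives placebo as its randomized comparator after Week 12, and the plots show descriptive mean and SE by group.

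Fourth, the SAP does not say outright that one model holds all six arms. One ANCOVA per visit yielding LS means by treatment group is the natural reading, but whether secukinumab is included is an inference. Leaving it out changes little: at m = 10, s = 35, V = (255.4 + 1225)/5 = 296.1, and r for 30 mg versus 120 mg (x6) is √(296.1/64.0) = 2.15.

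The planned residual check does not answer the point, because it has no consequence.

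**Conclusion.** The concern holds for the later visits up to Week 12. The SEs, CIs and p-values of the percent-PASI ANCOVA can be miscalibrated for a reason visible in the plan's own response rates, and no remedy is pre-specified.

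Under the assumed SDs, the SE for 30 mg versus 120 mg (x6) is about 1.0 to 2.0 times its true value, with loss of power. Intervals against placebo usually cover about 79-95%. Both directions are conditional: the second needs a placebo SD clearly above the active SDs (above about 21-26 for 120 mg (x6), depending on the active SDs assumed), and the first can fail for individual dose pairs when placebo's SD is no larger than theirs.

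The primary IGA analysis and the PASI 75/90/100 responder analyses by CMH are untouched, and the Week 12 conclusion against placebo did not change in any simulation. This should be corrected, but it does not threaten the main result.

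**What to change.** In SAP 4.2.2.2.3, make this the planned method for percent PASI change: the same ANCOVA (treatment, prior biologic use, weight stratum, baseline) with a separate residual variance for each arm. In SAS this is `PROC MIXED` with `REPEATED / GROUP=treatment` and Satterthwaite or Kenward-Roger degrees of freedom. Heteroscedasticity-consistent SEs are an acceptable alternative. Name one of the two in the text, before the Week 12 contrasts are seen by whoever chooses, so that the residual check becomes descriptive and does not select the method. The multiple-imputation analysis in SAP 4.1.1.4.2 refers to this section and would follow it.

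The cost is one sentence and one program option. The factors and covariate in Protocol 9.4.1 stay as they are. The downside is slightly fewer degrees of freedom and, if placebo is the most variable arm, somewhat wider intervals against placebo. The method stays valid whichever way the unknown SDs fall.
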